4.5.3 Withdrawal case management

In the case of the withdrawal from the trial, the researchers should actively take measures to complete the final examination as soon as possible to analyze the efficacy and safety. All trial cases should be completed in the case report form and the reasons for the withdrawal.

5 Suspension test standard

The discontinuation test means that the clinical trials have not been completed by the end of the program. The purpose of the suspension test is to protect the rights and interests of the subjects, to ensure the quality of the test and to avoid unnecessary economic losses. Standard for discontinuation of a test:

1) serious safety problems in the test, should promptly stop the test.

2) The trial found that the drug did not have clinical value and should discontinue trials, on the one hand, to avoid delaying the effective treatment of the subjects while avoiding unnecessary economic losses.

3) In the experiment, it was found that the clinical trial program had major errors and

it was difficult to evaluate the effect of the drug; or a well-designed design, which made important deviations in the implementation, and continued, it is difficult to evaluate the effect of the drug.

4) The applicant asked for a suspension (such as funding reasons, management reasons, etc.).

6 Treatment Plans

6.1 Experimental medication

6.1.1 Drug delivery

Test drug: vitamin K1 for injection, specification: 10mg each

Contrast drug: normal saline.

All trials were administered by the investigators in a single blind manner,.

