1.3 Possible risks

Adverse reactions of vitamin K1: occasionally allergic reactions. Mainly occurs when the intravenous injection is too fast, more than 5mg/ minutes can cause facial flushing, sweating, bronchospasm, tachycardia,

hypotension, etc., serious allergic reactions may endanger life. Intramuscular injection can cause redness and swelling. The newborn may suffer from hyperbilirubinemia, jaundice and hemolytic anemia after the use of the product.

.1.4. Benefits

Cerebral hemorrhage is a common disease in Department of neurosurgery. It is an important measure to reduce the mortality and disability rate in the acute stage. Vitamin K1 may reduce the risk of rebleeding in patients with intracerebral hemorrhage, and the amount of brain bleeding is directly related to prognosis. Effectively reduce the amount of intracerebral hemorrhage, improve the prognosis, reduce the length of stay, reduce the time of admission to ICU and reduce the mortality.

2 Test purpose

The effectiveness and safety of vitamin K1 were mainly targeted at patients with cerebral hemorrhage (non aneurysm or vascular malformations, rupture, bleeding). To observe whether vitamin K1 can effectively avoid the increase of cerebral hemorrhage and improve the prognosis.

3 Test design

The study included spontaneous hypertensive intracerebral hemorrhage at super tentorium of cerebellum patients as the research object, to exclude cerebral aneurysms or cerebral hemorrhage, venous malformation of abnormal liver function, taking anticoagulants or antiplatelet drugs in patients. The study was divided into the experimental group and the control group, and a multicenter randomized controlled trial was conducted. In the use of a etamsylate intravenous infusion of 0.5g of patients admitted to hospital within 8 hours later, the experimental group in the incidence of cerebral hemorrhage within 2 days after the daily intravenous infusion of vitamin K1 20mg, the control group received intravenous saline, all patients were no longer use other hemostatic agents. The efficacy and safety of vitamin K1 in the early onset of cerebral hemorrhage were assessed by the observation between two groups.

A randomized, single blind, positive / placebo parallel control, multicenter, clinical trial design was used. The treatment lasted for 2 days and followed up for 6 months.

4 Subjects recruited and exited

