6.1.3 Preparation

The study nurse assigned the experimental drug according to the instruction manual in the kit. Before using, add the test medicine to 100ml 0.9% Sodium Chloride Injection and shake it well.

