6.1.4 Route of administration

Basic treatment: all subjects according to the routine treatment of cerebral hemorrhage, the use of Phenol ethylamine intravenous 0.5g within 8 hours after admission, another program in accordance with the "Neurosurgery of Wang Zhongcheng", including the surgical removal of hematoma and drainage, conservative treatment, control of intracranial pressure, prevention of complications.

Test group:

Normal saline 100ml+Vitamin K1 20mg, Once a day, intravenous drip, two days in

hospital.

Control group:

Normal saline 102ml, Once a day, intravenous drip, two days in hospital.

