7.1 Test program evaluation

①Demographic data: age, sex, and ethnic group.

⁽²⁾History: ask for or collect current and past medical history based on existing medical records.

③Medication history: before taking the test, take the prescription or over-the-counter drugs, and record the generic name, daily total dose, usage and cause of use of the drug.
④The diagnosis of disease was confirmed by CT or MRI, and the amount of cerebral hemorrhage was calculated at the later stage (after the onset of the disease, the examination was not repeated).

⁽⁵⁾Physical examination: vital signs include body temperature (Ye Wen), respiration, heart rate, and blood pressure.

⁽⁶⁾Assessment of biological specimen collection and laboratory: collected blood and urine of Hematology, serum biochemistry, pregnancy test and laboratory examination, biological specimens from all participating units of the laboratory is responsible for collecting, processing, preservation and detection. Prior to the signing of the test drug, the clinical trial participant shall provide the bid with the normal reference range of the laboratory indicators. If there is any change during the test period, the applicant shall be promptly informed of the bid.

⑦Scale evaluation: mRS score.

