7.3 Follow-up visit

1 months (+ 3 days) and 6 months (= 3 days) after the onset of intracerebral hemorrhage: the researchers performed a mRS score using telephone follow-up.

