9.3 Handling and recording of adverse events

9.3.1 Treatment for adverse events

Inpatient

If the subject has adverse events during hospitalization, follow the following procedures:

Found adverse events in subjects, tube bed doctor or the doctor on duty shall promptly inform researchers, if necessary, can be the first symptomatic treatment, the degree of correlation between classification by research physician preliminary assessment of adverse events and drug test, and give further advice:

- ① General adverse events: can closely observe the outcome of the event or the corresponding symptomatic treatment;
- ② Important adverse events: physicians should promptly inform major researchers, and pause treatment, adjust drug dosage and targeted treatment according to the subjects' condition;
- ③ Serious adverse events: follow "9.4" for processing and reporting.
- ④ According to the patient's treatment, if the subject's injury exceeds the capacity of the research department, the relevant department should be invited to consult and assist in the treatment.

Outpatient

The adverse events that the subjects after the study, physicians should ask detailed subjects at the time of the symptoms and signs and place, the necessary explanation and

guidance on the subjects, and the degree of correlation of adverse events and give preliminary evaluation; as the subjects in the local medical institutions, contact by telephone and reception the doctor, check again the degree of adverse events and give treatment advice:

 General adverse events: initial visit to local hospital and notification of outcome of close observation;

⁽²⁾ Important adverse events: recommend returning to the hospital for treatment or to the local hospital for treatment, and timely notification of the main researchers, such as limited local hospitals, doctors should be sent to the treatment. An emergency envelope is also provided for emergency blind use (if applicable). According to the plan request, adopts the pause treatment, adjusts the medicine dosage and the symptomatic treatment and so on.

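### The plan does not say who is masked and specifies no masked assessment for CT haematoma volume or telephone mRS, its two decisive outcomes

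*Protocol*

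**What the plan says.** **Blinding.** Protocol section 3 (Test design) states: "A randomized, single blind, positive / placebo parallel control, multicenter, clinical trial design was used". Section 6.1.1 adds: "All trials were administered by the investigators in a single blind manner". Neither says which parties are masked.

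**Preparation and unblinding.** Section 6.1.3 says "The study nurse assigned the experimental drug according to the instruction manual in the kit". Section 6.1.4 gives the test infusion as "Normal saline 100ml+Vitamin K1 20mg" and the control as 102 ml of saline. Section 9.3.1, in its outpatient text, says "An emergency envelope is also provided for emergency blind use", followed by a qualifier that makes it conditional.

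**Assessment.** Section 7.3 says that at 1 and 6 months "the researchers performed a mRS score using telephone follow-up". Section 7.1, item 4, says "the amount of cerebral hemorrhage was calculated at the later stage". Section 4.2 names the Duotian formula for volume. No CT reader is named, and masking is not mentioned for the mRS rater or the reader.

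**Role of the two outcomes.** Section 8 of the protocol makes haemorrhage volume at days 0, 1, 3 and 7 the main outcome. The SAP, sections 3(2) and 5(5)1, rests the superiority conclusion on mRS change from baseline, with the covariance analysis at 6 months.

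**The concern.** Single blind usually means that the patient is masked and the investigator is not. If that is meant here, nothing in the plan keeps knowledge of the arm away from the people who produce the two outcomes that decide the trial.

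Both outcomes need judgement. The mRS is graded from a telephone conversation. A formula-based volume depends on what the reader measures on the image. The protocol acknowledges this measurement problem itself: section 4.3 excludes irregular and intraventricular haemorrhage because the volume cannot be measured accurately.

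Reading error that is equal in both arms costs only precision. Error that differs by arm shifts the treatment difference. The SAP's ANCOVA adjusts for baseline, centre and operation, and none of these carries information about how a rater scored one arm relative to the other. The shift would therefore remain in the estimate and could not be removed after the data are collected.

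**Working it through.** **Step 1. What the text settles.**

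| Question | Where | Answer in the documents |
|---|---|---|
| Who is masked? | Protocol 3, 6.1.1 | Single blind; parties not defined |
| Who assigns and mixes the drug? | 6.1.3 | Study nurse, from a kit; coding of kits not described |
| Are the infusions alike? | 6.1.4 | 100 ml plus drug against 102 ml, which suggests volume matching; appearance not described |
| Is there an unblinding route? | 9.3.1 | Emergency envelope, mentioned once and conditionally |
| Who scores mRS? | 7.3 | Researchers, by telephone; masking not stated |
| Who measures volume? | 4.2, 7.1 | Not stated; formula only |

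The middle rows fit poorly with the usual meaning of single blind: an emergency envelope has little use for a clinician who already knows the arm. So either investigators are unmasked and the outcomes are unprotected, or they are masked and the label misleads. Both cases need a change to the text.

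**Step 2. Sensitivity of the test to differential assessment.** There is no figure in the plan to reproduce, because the documents state no sample size, SD or effect size. From the SAP come only the one-sided level of 0.025 and its critical value of 1.96. All other inputs below are assumptions.

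For an unadjusted two-sample comparison with no true effect and a bias b in the direction that the test counts as success:

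error = 1 − Φ(1.96 − b / SE), with SE = SD × √(2/n) and n per arm.

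*No bias:* b = 0 gives 1 − Φ(1.96) = 0.025.

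*mRS:* a one-grade favourable shift in 10%-20% of one arm gives b = 0.10 × 1 = 0.1 to 0.20 × 1 = 0.2 points.

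- Low end, n = 100, SD 2.0, b = 0.1: SE = 2.0 × √0.02 = 0.283; b/SE = 0.354; error = 1 − Φ(1.606) = 0.054.
- High end, n = 200, SD 1.5, b = 0.2: SE = 1.5 × √0.01 = 0.150; b/SE = 1.333; error = 1 − Φ(0.627) = 0.265.

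*Volume:* a systematic 1 ml reading difference, tested at the same level for illustration.

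- Low end, n = 100, SD of change 8 ml: SE = 8 × √0.02 = 1.131; b/SE = 0.884; error = 1 − Φ(1.076) = 0.141.
- High end, n = 200, SD of change 6 ml: SE = 6 × √0.01 = 0.600; b/SE = 1.667; error = 1 − Φ(0.293) = 0.385.

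**Step 3. The same check without assuming an SD.** With bias in SD units, the one-sided error becomes:

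| n per arm | 0 SD | 0.1 SD | 0.2 SD | 0.3 SD |
|---|---|---|---|---|
| 50 | 0.025 | 0.072 | 0.169 | 0.323 |
| 100 | 0.025 | 0.105 | 0.293 | 0.564 |
| 200 | 0.025 | 0.169 | 0.516 | 0.851 |

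For a fixed bias, the inflation grows with sample size, so a larger trial gives no protection.

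**The case against.** The strongest reply is that the plan does not show unmasked assessment; it is silent. Several stronger readings are tempting, and the documents do not support them:

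- *Investigators know the arm.* This is inferred from the usual meaning of single blind. The kit and the envelope point the other way.
- *The people who give the drug also score mRS.* Section 6.1.1 speaks of investigators and section 7.3 of researchers. In a translated multicentre protocol these may or may not be the same individuals.
- *Investigators measure the CT volumes.* No reader is named anywhere.
- *Full masking needs no extra staff.* Staffing is not described, kits are not said to be coded or identical, and the envelope is conditional. A separate caller or a move to double blinding could need resources that the text does not show.

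The calculation is also open to challenge. Sample size, SDs and bias are all assumed. The test is unadjusted, whereas the SAP specifies ANCOVA. The one-sided 0.025 test is defined for mRS only; volume is simply compared. The SAP declares superiority if the interval lies above zero without stating the direction of subtraction, so the formula has to assume which way counts as success.

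Finally, the remark in section 7.1 about later calculation is hard to read, and eligibility under section 4.2 needs a volume between 10 and 45 ml at enrolment. Baseline volume therefore cannot be left entirely to later reading.

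All of this stands, and it limits the point to an omission. It does not answer the omission: neither document specifies masked assessment for either outcome.

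**Conclusion.** The concern holds as a gap in specification. The protocol does not define who is masked, its references to blinding do not fit together, and nothing protects haematoma volume or 6-month mRS from assessment that differs by arm.

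The size cannot be established from the documents. Under the stated assumptions, the one-sided error moves from 0.025 to about 0.05-0.27 for mRS, and to about 0.14-0.39 for volume if it were tested at that level. A reader might take these figures as evidence that the trial's results would be biased. They are not: they show only that modest differential assessment would be enough to undermine the test. The change is worth making because the exposure covers both decisive outcomes, cannot be repaired at analysis, and can be reduced at modest cost.

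**What to change.** 1. **Section 7.1.** Require that outcome volumes from the CTs already scheduled be measured by the existing readers on coded images, with arm and patient identity hidden. The baseline volume needed for eligibility is still read at enrolment, and is re-read with the coded batch so that all analysed volumes come from the same process.
2. **Section 7.3.** Require a fixed script for the mRS call. Where existing site staff allow, the caller should be someone who did not prepare or give that patient's infusion and has no access to the allocation. Record for each call whether the rater knew the arm.
3. **Sections 3, 6.1.1, 6.1.3 and 9.3.1.** Reconcile these by stating who is masked: patient, treating investigator, preparing nurse, mRS rater and CT reader. State also whether the kits are coded and when the emergency envelope applies.

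**Cost.** Item 1 needs image coding and one baseline re-read per patient, but no new scan and no new person. Item 2 needs some scheduling effort, mainly at small sites, which is why the separate caller depends on staffing. Item 3 is a text change.

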6.1.2 Drug storage and stability

Test drug storage conditions: shading, airtight, cool and dry place to preserve.

6.1.3 Preparation

The study nurse assigned the experimental drug according to the instruction manual in the kit. Before using, add the test medicine to 100ml 0.9% Sodium Chloride Injection and shake it well.

6.1.4 Route of administration

Basic treatment: all subjects according to the routine treatment of cerebral hemorrhage, the use of Phenol ethylamine intravenous 0.5g within 8 hours after admission, another program in accordance with the "Neurosurgery of Wang Zhongcheng", including the surgical removal of hematoma and drainage, conservative treatment, control of intracranial pressure, prevention of complications.

Test group:

Normal saline 100ml+Vitamin K1 20mg, Once a day, intravenous drip, two days in

hospital.

Control group:

Normal saline 102ml, Once a day, intravenous drip, two days in hospital.

6.1.5 Test cycle

Medication for 2 days + followed up for 6 months.

7 Test procedure and plan

7.1 Test program evaluation

①Demographic data: age, sex, and ethnic group.

⁽²⁾History: ask for or collect current and past medical history based on existing medical records.

③Medication history: before taking the test, take the prescription or over-the-counter drugs, and record the generic name, daily total dose, usage and cause of use of the drug.
④The diagnosis of disease was confirmed by CT or MRI, and the amount of cerebral hemorrhage was calculated at the later stage (after the onset of the disease, the examination was not repeated).

⁽⁵⁾Physical examination: vital signs include body temperature (Ye Wen), respiration, heart rate, and blood pressure.

⁽⁶⁾Assessment of biological specimen collection and laboratory: collected blood and urine of Hematology, serum biochemistry, pregnancy test and laboratory examination, biological specimens from all participating units of the laboratory is responsible for collecting, processing, preservation and detection. Prior to the signing of the test drug, the clinical trial participant shall provide the bid with the normal reference range of the laboratory indicators. If there is any change during the test period, the applicant shall be promptly informed of the bid.

⑦Scale evaluation: mRS score.

7.2 Test procedure

Subject to any test procedure, the subjects, legal agents and / or subjects must have read and signed an informed consent letter approved by the ethics committee. The test

procedure shall be carried out within the prescribed time window of the visit, as detailed in the test flow chart.

7.3 Follow-up visit

1 months (+ 3 days) and 6 months (= 3 days) after the onset of intracerebral hemorrhage: the researchers performed a mRS score using telephone follow-up.

7.4 Unscheduled visit

During the trial, unplanned visits should be made if the subject is unwell.

7.5 Test flow chart

			treat	ment		vi	st
Time point	(D0)	D1	50	D7	Discharge	The first	The six
		DI	50	וע	or death	month	month
Collect basic inf	ormation	-	-		_	-	
informed consent	\checkmark						
Inclusion Criteria	\checkmark						
History	\checkmark						
acquisition							
General	\checkmark						
information							
Check item	Γ	ľ	T	T	T	r	1
temperature	\checkmark			\checkmark			
Vital signs	\checkmark			\checkmark			
Cerebral	\checkmark		\checkmark	\checkmark	\checkmark		
hemorrhage							
volume (CT)							
GCS						\checkmark	\checkmark
Drugs and	\checkmark	\checkmark	\checkmark				
dosages							
24h intake and	\checkmark						
output							
Blood routine,	\checkmark		\checkmark	\checkmark	\checkmark		
liver and kidney							
function,							
electrolyte	1	1					
Platelet							1
Coagulation				\checkmark	\checkmark	\checkmark	\checkmark
function	1	1	1		1	1	1
Complications	N	V	N	N	N	N	\checkmark
and adverse							
reactions						1	1
MRS						N	N
ICU total							

	hospital stay
--	---------------

7.5 Concomitant medication and treatment

7.5.1 Basic treatment

Allow the cerebral hemorrhage treated with conventional therapy control of intracranial hypertension, prevention of complications, but it must be the case report form to record the medicine general or other treatment, dosage, reason, use frequency and time etc, so as to summarize, analyze and report.

7.5.2 No medication or treatment

During the period of medication and during the follow-up period, drugs that affect the efficacy of the regimen may not be used, such as antithrombotic or anticoagulant or hemostatic drugs.

7.5.3 Medication and treatment are permitted

(1) The other combined diseases without affecting the curative effect and safety evaluation, can be symptomatic medication, but it must be the case report form to record the medicine general or other treatment, dosage, reason, use frequency and time etc, so as to summarize, analyze and report.

⁽²⁾The follow-up period can use cognitive rehabilitation methods, including occupational therapy, implicit memory rehabilitation, errorless learning, cognitive neuropsychological rehabilitation, rehabilitation and computer assisted cognitive rehabilitation, virtual remote control via the Internet, and the electromagnetic stimulation, should be recorded in detail in CRF.

⁽³⁾The combination drugs used for adverse events during the trial should be recorded in CRF.

8 Therapeutic evaluation standard

Main outcome measures: the amount of intracerebral hemorrhage (0d, 1D, 3D, 7D) at each time after the onset of disease.

Main outcome measures: (1) the amount of the time changes in blood coagulation, platelet levels and GCS scores after the onset (0d, 1D, 3D, 7D); (2) days in ICU; (3) the total hospitalization days; (4) complications including neurological complications, complications, blood coagulation circulatory complications after cerebral hemorrhage; (5) 1m and 6m mRS score.

9 Safety evaluation

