Statistical analysis plan

1. Statistical software

Using STATA version 12.0 statistical software.

2. Special data processing

(1) Missing data: When a certain important data due to loss, miss follow-up, examination is happen, the LOCF method will be adopted to carry out the data and the secondary index will not be transferred.

(2) Outlier data: According to statistical and medical analysis, determine these data will be included or not. Sensitivity analysis was conducted for the outliers of the main targets, including two results consistent with those who did not outliers.

3. Selection of inspection level α and power of test β

(1) Difference test: With $\alpha = 0.05$ as the test standard, two-sided test was adopted, and the statistical methods, statistics and specific P values were given. $P \leq 0.05$ was considered statistically significant.

(2) Superiority test: Based on a power of 80% ($\beta = 0.2$), $\alpha = 0.025$ was conducted for the one-sided test. The difference between the groups and the 95% confidence interval of the mRS score difference to the baseline values after treatment in the experimental group and the placebo group was calculated by the least square method. If the 95% confidence interval between the two groups was greater than 0, the experimental group can be thought to be superior to the placebo group, otherwise not.

4. Statistical expression

(1) The statistical report mainly expressed in form, which was self-evident. It had the title, the heading and the number of cases, the necessary remarks and the text of statistical results and the description of data results.

(2) Descriptive statistics: The measurement data is described by mean number, standard deviation, maximum value, minimum value, 95% confidence interval, median, Q1 and Q3. The enumeration data is described by frequency (constituent

ratio), and corresponding statistics and P value are calculated.

(3) Inferential statistics: Measurement data were compared between groups by analysis of variance or K-W rank-sum test according to the distribution pattern. Enumeration data were compared between groups by R*C Chi-squared test and Fisher exact test. The ranked data was tested by CMH. The main/important therapeutic effect index will use the baseline for the covariant, considering center, operation or not after injury for analysis of covariance.

5. Specific statistical analysis content

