(1) Analysis of program implementation: a list was adopted to summarize the entry and completion of all and each central cases, and tabulate details and the data collation of those cases which are not meet the inclusion criteria, fall off, low compliance, against therapy and drug combination, interview time beyond window.

(2) Analysis the patient compliance and the drug combination during the trail.

(3) Condition of each analysis data set: Based on the analysis of the implementation of the program, determining the data imputation of each deviated test programme case. Summarize the cases of each analysis data sets, such as per-protocol set (PPS), full analysis set (FAS), safety set (SS).

(4) Baseline equalization analysis: Compare the baseline data of demographic data, vital signs and medical history related features.

(5) Analysis of curative effect index :

1) Compare the changes of mRS score to the baseline after using the drug in 2 days, followed up with 1 month and 6 months in the two groups. The main/important therapeutic effect index will use the baseline for the covariant, considering center, operation or not after injury for analysis of covariance. The covariance analysis was performed on the change of mRS score at baseline after 6 months of follow-up. The difference between the groups and the 95% confidence interval of the mRS score difference to the baseline values after treatment in the experimental group and the placebo group was calculated by the least square method. If the 95% confidence interval between the two groups was greater than 0, the experimental group can be

thought to be superior to the placebo group, otherwise not.

2) Compare the changes of cerebral hemorrhage amount to the baseline in the two groups.

3) Compare the changes of coagulation function, platelet level and GCS score to the baseline in the two groups.

4) Compare the number of days stayed in the ICU and the hospital in the two groups.

(6) Safety analysis:

Compare the incidence and classification rate of complications, adverse events and adverse reactions during the test in the two groups, and list the details of each adverse event, such as the detailed occurrence, outcome and the relationship with drugs.

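### Protocol and SAP name no shared primary endpoint or time: the protocol leads with haematoma volume on no deciding day, while the SAP's only superiority rule is on mRS change

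*Protocol*

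**What the plan says.** **Protocol.** Section 8 has two lists, both headed as main outcomes. The first holds haematoma volume only: "Main outcome measures: the amount of intracerebral hemorrhage (0d, 1D, 3D, 7D) at each time after the onset of disease". No day is singled out and no contrast is defined. The second begins "Main outcome measures: (1) the amount of the time changes in blood coagulation, platelet levels and GCS scores after the onset" and goes on to ICU days, hospital days and complications, with mRS at 1 and 6 months as its fifth and last item. Section 2 gives a double aim without ranking: "To observe whether vitamin K1 can effectively avoid the increase of cerebral hemorrhage and improve the prognosis".

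**SAP.** Section 3(2), which begins "Superiority test: Based on a power of 80" per cent, sets one-sided alpha at 0.025 and applies the test to mRS change from baseline. The decision rule is: "If the 95% confidence interval between the two groups was greater than 0, the experimental group can be thought to be superior". Section 5(5)1) repeats the rule. It compares mRS change at 2 days, 1 month and 6 months, and then adds: "The covariance analysis was performed on the change of mRS score at baseline after 6 months of follow-up". Volume appears in section 5(5)2) as a comparison of change from baseline, with no day. Section 4(3) gives a model for an undefined main or important index, with baseline as covariate and "considering center, operation or not after injury for analysis of covariance". On missing data, section 2(1) says: "the LOCF method will be adopted to carry out the data and the secondary index will not be transferred".

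**The concern.** A trial needs one prespecified answer to what counts as success. The protocol's first main outcome has no deciding day and no superiority rule. The outcome that has the rule stands last in the protocol's second list. If volume is favourable and 6-month mRS is not, or the reverse, the sponsor could claim success from one document while a critic denies it from the other.

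Three further parts of the plan depend on the missing definition:

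- The 80% power is not tied to the protocol's first main outcome.
- LOCF is applied or withheld according to whether a variable is secondary, and neither document settles that for volume or mRS.
- If the choice of endpoint or day stays open until the data are seen, the nominal error rate no longer applies.

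**Working it through.** **1. The two documents side by side**

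| | Haematoma volume | mRS |
|---|---|---|
| Protocol 8 | First main outcome; days 0, 1, 3, 7; no deciding day | Last item of second list; 1 and 6 months |
| SAP 3(2) | Not mentioned | Superiority rule, one-sided 0.025, 80% power; no time given |
| SAP 5(5) | Item 2: compared with baseline; no day, no success rule | Item 1: 2 days, 1 month, 6 months; covariance analysis at 6 months; rule repeated |

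**2. Does any reading reconcile them?**

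- *The second heading in protocol 8 is a slip for secondary.* Volume is then the sole main outcome and mRS is secondary, yet the only superiority rule is on mRS.
- *Both lists are main.* There are then many main outcomes at several times, with no hierarchy and no multiplicity rule in either document.
- *The SAP governs.* Neither document says so, and the SAP never calls mRS primary.
- *The aim decides.* Protocol section 2 names both bleeding and prognosis.

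None of these yields one shared endpoint and time.

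**3. Alpha levels.** The two-sided 0.05 of SAP 3(1) and the one-sided 0.025 of SAP 3(2) give the same critical value, 1.960. The conflict is about the endpoint, not the level.

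**4. Illustration of error inflation.** This applies only if success on any one route could carry the claim, which neither document says. The test statistics are taken as multivariate normal with mean zero, and the rate is P(at least one exceeds 1.96), from 4,000,000 draws per case. The correlations are assumptions: r_v = 0.5 to 0.9 among volumes and r_m = 0 to 0.5 between volume and mRS. An exact check for one volume day plus mRS at r_m = 0 gives 1 − 0.95² = 0.0975 two-sided and 1 − 0.975² = 0.049 in the favourable direction.

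| Routes to a claim | Favourable direction (nominal 2.5%) | Two-sided (nominal 5%) |
|---|---|---|
| One volume day + 6-month mRS | 4.5%–4.9% | 9.1%–9.8% |
| Days 3 and 7 + mRS | 5.4%–6.9% | 10.8%–13.6% |
| Days 1, 3 and 7 + mRS | 6.0%–8.6% | 12.0%–16.9% |
| Volume only, days 3 and 7 | 3.5%–4.5% | 7.0%–9.1% |
| Volume only, days 1, 3 and 7 | 4.2%–6.3% | 8.4%–12.5% |

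The rows with day 1 are doubtful, because the flow chart, damaged in extraction, shows no clear CT mark on that day. Only 6-month mRS is counted here; allowing the SAP's other two mRS times would raise the rates.

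**5. Power.** The documents show no sample size, effect size or SD, so the 80% cannot be reproduced for either endpoint.

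**The case against.** The strongest reply is that the SAP in practice points to 6-month mRS. The sentence on the main or important index is repeated inside the mRS item, directly before the 6-month covariance analysis, and the only success rule in either document is on mRS. On that reading there is one test at one-sided 0.025. That is a fair inference, but the same sentence also stands in SAP 4(3) as a general rule. The SAP also lists 2-day and 1-month mRS, and SAP 3(2) gives no time. Nor does the inference remove the protocol's placing of volume first.

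Other points stand in part:

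- Volume is not without an analysis. If it is the main index, SAP 4(3) gives it a covariance model and SAP 2(2) an outlier sensitivity analysis. The general two-sided 0.05 test also applies. What it lacks is a deciding day and a superiority rule.
- The protocol states no success rule of its own, so opposite verdicts are a possible reading and not something either document prescribes.
- The error rates rest on assumed correlations and on success by any route. For a superiority claim the favourable-direction column is the relevant one. The finding does not depend on these rates.
- Missing ticks in the damaged flow chart are weak evidence. Its GCS row also shows only months 1 and 6, although section 8 requires GCS on days 0 to 7. The lack of a dated baseline mRS is supported independently by protocol 7.3 and 8.
- Several items in the fix could be raised separately. They are included because each depends on which endpoint is chosen.

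**Conclusion.** The concern holds and must be fixed. The two documents contradict each other on which endpoint decides the trial, and neither sets volume to a day. This follows from the text alone and needs no assumption.

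The statistical cost depends on how the gap is closed. If the SAP rule on 6-month mRS alone governs, the false-positive rate for a favourable claim stays at 2.5%. If the choice stays open until results are known, the illustration gives 4.5% to 4.9% for one volume day plus 6-month mRS. It gives up to 6.9% with days 3 and 7, and up to 8.6% if day 1 also counts. The 80% power statement cannot be credited to either endpoint until a derivation is shown.

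**What to change.** 1. Name the same single primary endpoint and time in protocol section 8 and SAP 3(2) and 5(5): either volume change from day 0 to one fixed day with a scheduled CT, or 6-month mRS. Head the remaining outcomes as secondary and state that the efficacy claim rests on the primary alone.
2. State the contrast as placebo minus experimental in change from baseline. The rule that the interval lies above 0 has no subtraction order. Lower volume is favourable, as is lower mRS on its usual scoring (the documents give no direction).
3. Adjust the primary model for baseline and centre. Include operation status only if it is fixed before randomisation, which the documents do not show.
4. If volume is chosen, state how volumes measured after surgical haematoma removal, which protocol 6.1.4 allows, are analysed.
5. If mRS is chosen, clarify whether the undated mRS item in protocol 7.1 is a baseline score, since 7.3 and 8 give only 1 and 6 months. If it is not, analyse the 6-month score itself.
6. Name the endpoint to which LOCF in SAP 2(1) applies, and derive the power for the chosen primary.

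**Cost.** Wording in protocol section 8 and SAP 2(1), 3(2), 4(3) and 5(5), possibly one clarification in protocol 7.1, and a power derivation. To show how much that derivation depends on the effect, n per arm = 2(1.960 + 0.842)²/d² gives 393, 175, 99 or 63 for an assumed standardised difference d of 0.2, 0.3, 0.4 or 0.5. The price is that a result on any other endpoint or day can no longer carry the claim.
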